8.2 METHODS USED TO MINIMIZE BIAS

Due to obvious differences in the physical appearance of the test articles, double-blinding of the study medication is not possible. However, assessments of the ulcer debridement status relating to the presence of non-viable necrotic tissue (primary objective) will be carried out in a blinded fashion by two independent assessors using digital photographs identified only by the subject number and date. Blinded assessment is intended to limit the occurrence of conscious and unconscious bias in the assessment and interpretation of the endpoints. In addition, randomization will be sequential according to a pre-determined, computer-generated randomization schedule. In this way the Investigator will not be able to direct a particular subject to a particular treatment thus preventing treatment allocation bias. Ulcer measurements will be carried out using the ImageIQ EDCIQ mobile imaging system which will minimize subjectivity in theses assessments.

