This visit should occur no more than 7 days after the Screening Visit. Any subject who returns but does not qualify at this visit will be a screen failure and will not be randomized. Upon completion of all screening procedures and confirmation that the subject is eligible for the study, the Investigator or designee will randomize the subject using an electronic randomization system (www.sealedenvelope.com) to obtain the treatment assignment.

The day of the week (Monday, Tuesday, etc.) on which this visit occurs will set the weekly visit day for all subsequent assessments/visits (Study Visits 2 through 7) if the subject is randomized. A (± 1) day visit window will be allowed. If an assessment is not made on the original day of the week for Study Visits 2-7, subsequent visits should be scheduled on the original week day. To minimize differences in baseline ulcer size between the two groups, randomized subjects will be stratified by ulcer size determined at this visit [≥ 1.0 and ≤ 10.0 cm²; ≥ 10.0 and ≤ 64.0 cm²]. Once randomized, subjects will be assessed weekly for the duration of the treatment period (SV1 through SV7).

The following procedures will be completed:

- 1. Record any changes in general health and the use of concomitant medications.
- 2. If any adverse events are observed or reported, they must be recorded as instructed in Section 12, *Adverse Events*.
- Review laboratory results from the blood sample and all other inclusion/exclusion
 criteria.
 - If the blood test results qualify and all entry criteria are met, the subject may be randomized.
- Irrigate the wound with normal saline delivered at 4-15 psi using the Irrimax® device.
 (Sharp debridement is NOT allowed.)
- 5. Photograph the target ulcer using the ImageIQ EDCIQ mobile imaging system. The target ulcer area (cm²) and percentage of the target ulcer surface covered with necrotic, nonviable tissue will be determined by two independent reviewers using the ImageIQ EDCIQ mobile imaging system. The target ulcer area and percentage of necrotic, nonviable tissue must be assessed by at least one independent reviewer prior to the subject being randomized.

Note: If the area of the target ulcer is >64.0 cm², the subject must be screen failed and should not be randomized.

- 6. Assess the wound status using both the PUSH and WBS tools.

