- 1. Record any changes in general health and the use of concomitant medications.
- If any adverse events are observed or reported, they must be recorded as instructed in Section 12, Adverse Events.
- Record the number of dressing changes since the previous study visit and the amount of time spent daily dressing the ulcer.

Only if the ulcer remains open at this visit:

Irrigate the wound with normal saline delivered at 4-15 psi using the Irrimax[®] device.
 (Sharp debridement is NOT allowed.)

All subjects:

- 5. Photograph the target ulcer using the ImageIQ EDCIQ mobile imaging system. The target ulcer area (cm²) and percentage of the target ulcer surface covered with necrotic, nonviable tissue will be determined by two independent reviewers using the ImageIQ EDCIQ mobile imaging system. Closed ulcers will be photographed and designated as "closed".
- 6. Assess the wound status using both the PUSH and WBS tools.
- 7. Record the time spent assessing the ulcer.
- All females of child-bearing potential must undergo a urine pregnancy test upon completion or discontinuation from the study.
- 9. Return all used and unused study medication to a secure area for accountability
- Dismiss the subject from the study. Institute appropriate standard ulcer care for ulcers remaining open at the discretion of the Investigator.

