9.4.2 Percentage of Necrotic Tissue and "Complete Debridement"

All wound photographs will be reviewed in a blinded fashion, identified only by subject number, initials, and date of assessment by two independent reviewers. The reviewers will complete an assessment form providing the percentage of the ulcer covered by non-viable, neerotic tissue as measured using the ImageIQ EDCIQ mobile imaging system. In any case where one reviewer selects 0% or "complete debridement", and the second reviewer does not, the photograph will be re-reviewed at a consensus meeting.

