Further details, including model assumptions and diagnostics to be examined are included in the study SAP. The preceding analysis will be repeated using the Per Protocol Population.

Kaplan-Meier plots will be presented by treatment, baseline wound area strata, baseline percentage of nonviable tissue and ulcer duration (categorized) and also to represent all covariates with significant effects in the final survival analysis model. Individual plots for multiple factors will be generated where appropriate.

In addition, a sensitivity analysis will be performed to ensure that the efficacy findings are not reliant on assumptions made in either the analysis or derivations. For purposes of the sensitivity analysis, the time to confirmed complete debridement for those subjects discontinuing the treatment period prematurely will be censored at the maximum possible duration of treatment under the study protocol (42 days), rather than time of actual discontinuation. Lastly, the two sensitivity analyses defined in the proportion of subjects achieving complete debridement analysis will be repeated for the time to achieve complete debridement; in these cases the

censoring flag may be modified as detailed previously in the primary analysis, but the time in days will remain unchanged.

The percentage reduction in wound area over the 6-week treatment period and at each assessment visit

Wound area is defined as surface area as measured by the ImageIQ EDCIQ mobile imaging system at each assessment visit by two independent image reviewers. The percentage change in wound area over the 6-week treatment period is then defined as:

Percentage reduction in wound area over 6-week treatment period= $\left(\frac{Area_{SV1} - Area_{SV1}}{Area_{SV1}}\right) \times 100\right)$

In cases where the wound is closed in the opinion of the Investigator, the wound area will be imputed as 0 cm², resulting in a percentage reduction in wound area of 100%. In circumstances where the wound area is missing at the Study Visit 7 for subjects that have not withdrawn prematurely due to closure, the last observation carried forward (LOCF) method will be used.

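### Wound area is set to 0 cm² on the unmasked Investigator's opinion that the ulcer is closed, with no stated blinded confirmation or sensitivity analysis

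*Combined protocol and SAP*

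**What the plan says.** Section 10.3.2 gives the default source of the endpoint: "Wound area is defined as surface area as measured by the ImageIQ EDCIQ mobile imaging system at each assessment visit by two independent image reviewers". Section 9.4.2 adds the masking: "All wound photographs will be reviewed in a blinded fashion, identified only by subject number, initials, and date of assessment by two independent reviewers". Section 8.2 credits the imaging system with making the measurements less subjective: "Ulcer measurements will be carried out using the ImageIQ EDCIQ mobile imaging system which will minimize subjectivity".

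Section 10.3.2 then makes an exception for the best possible result. "In cases where the wound is closed in the opinion of the Investigator", it says, "the wound area will be imputed as 0 cm², resulting in a percentage reduction in wound area of 100" per cent. It attaches no further condition.

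The person whose opinion counts knows the treatment. Section 8.2 states: "Due to obvious differences in the physical appearance of the test articles, double-blinding of the study medication is not possible". Under Section 9.1.2, "the Investigator or designee will randomize the subject using an electronic randomization system" and so receives the assignment.

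Section 9.1.3 defines a closed ulcer as fully re-epithelialised, not draining and needing no dressing. A subject found closed goes straight to the exit visit and stops treatment. At that visit (Section 9.1.4), "Closed ulcers will be photographed and designated as" closed. Footnote c of Table 17-1 confirms that the photograph is required in that case too.

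**The concern.** An observer-blind trial relies on its masked readings. Here the area endpoint uses them except at its extreme value, where an unmasked judgement supplies the number. A mistaken closure call can only raise that subject's reduction, and if such calls are made more readily in one arm the treatment comparison shifts.

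Nothing later in the protocol would reveal a wrong call. The subject has left the study, so no later photograph exists. Closure before six weeks also satisfies the completion criterion for the Per Protocol population (Section 10.1), so an analysis in that population would not drop the case on that ground. Best-case and worst-case analyses are specified for complete debridement (Section 10.3.1) and for non-viable tissue (Section 10.3.2), but none is stated for wound area or closure.

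**Working it through.** **Does the imputation fill a gap in the data?** The exit photograph is taken for all subjects, closed ulcers included (Section 9.1.4; Table 17-1, footnote c). Images go to a central database for review (Section 9.4.1), and all photographs are read blinded (Section 9.4.2). A masked area reading is therefore feasible for every ulcer that exits as closed. The rule in 10.3.2 depends only on the Investigator's opinion.

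**Which endpoints are affected?** Primary debridement status comes from the two blinded reviewers, with a consensus meeting where they disagree (Sections 9.4.2 and 10.3.1). The imputation applies to percentage reduction in wound area only.

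**How large is the effect?** The plan gives no power, standard deviation or closure rate for wound area, so there is no stated figure for this endpoint to reproduce. The inputs are:

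- n = 16 per arm randomised (Section 11). This follows from 26 required subjects, or 13 per arm: 13/0.85 = 15.3, rounded up to 16, and 2 × 16 = 32.
- n = 13 per arm if only the 26 required subjects are analysed.
- True reduction r in an ulcer wrongly called closed. The documents give no value, so a range is assumed.

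One mistaken call raises its arm's mean by (100 − r)/n percentage points:

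| Assumed r | One call, n = 16 | Three calls in one arm, n = 16 | One call, n = 13 |
|---|---|---|---|
| 99% | 1/16 = 0.06 | 0.19 | 0.08 |
| 95% | 5/16 = 0.31 | 0.94 | 0.38 |
| 90% | 10/16 = 0.63 | 1.88 | 0.77 |
| 80% | 20/16 = 1.25 | 3.75 | 1.54 |

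These are shifts in an unadjusted arm mean. Equal numbers of similar mistaken calls in two arms of equal size cancel in the difference.

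**Which rows are plausible?** The area left open is (1 − r/100) × baseline area. At r = 80% this is 0.2 cm² for a 1.0 cm² ulcer, 2.0 cm² for a 10 cm² ulcer and 12.8 cm² for a 64 cm² ulcer. The last two are hard to reconcile with the Section 9.1.3 definition. At r = 95% the areas are 0.05, 0.5 and 3.2 cm². Honest borderline calls belong mostly in the upper rows of the table.

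**Compared with sampling error.** With an assumed standard deviation of 20 to 40 points, the standard error of the difference at 16 per arm is SD × √(2/16), which is 7.1 to 14.1 points. One call is small against that. Three calls in one arm at r = 80% (3.75 points) would be roughly a quarter to a half of a standard error.

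**The case against.** The strongest reply is that closure has a written definition under which the open area is zero, so entering 0 cm² only applies the definition. That stands as a limit on discretion. It does not change who applies the definition: someone who knows the arm, without confirmation.

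A reader might infer that the Investigator's opinion overrules a blinded measurement already made. The text does not establish this. Section 9.1.4 can be read to mean that no area is traced once an ulcer is designated closed. The next sentence of 10.3.2 restricts last observation carried forward for a missing Visit 7 area to subjects who did not leave because of closure, which fits a zero entered so that the value is not missing. Section 9.1.4 also has the reviewers determine area for all subjects, so the point is ambiguous. On either reading the value analysed rests on the unmasked call. Nor does 9.1.4 say who makes the closed designation; it need not be the site.

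A reader might also infer that no analysis anywhere checks the call. Sections 10, 10.2 and 10.3.2 leave detail to a separate SAP whose text is not in the document reviewed. What can be said is that the protocol states no check.

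Section 8.2 ties blinding to debridement status; its sentence on ulcer measurement credits the imaging system. The case for masked area readings therefore rests on Section 9.4.2 read with 10.3.2.

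Finally, drainage and the need for a dressing cannot be seen in a photograph. This is true of closure as a clinical state, but the endpoint is surface area, which the plan already assigns to image readers.

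**Conclusion.** The point holds as a low-cost improvement. For one secondary endpoint, an unmasked opinion supplies the most favourable value although a blinded reading could be had from a photograph already required, and the protocol states neither confirmation nor a sensitivity analysis.

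The likely size is small: about 0.06 to 0.6 points per mistaken call at 16 per arm for assumed true reductions of 99% to 90%, and 1.25 points at 80%, a case that sits badly with the closure definition except in the smallest ulcers. It becomes material only if several such calls fall in one arm. The number of closures is unknown and could be zero.

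The documents do not show that the rule would favour SANTYL; the risk is unequal calls by an assessor who knows the treatment. The primary endpoint is untouched, and no figure stated in the plan is wrong on this account.

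**What to change.** Have both image reviewers record area from every exit photograph, including ulcers called closed, without sight of any closed designation. Say how their two area readings are combined; 10.3.2 specifies a mean for non-viable tissue but gives no rule for area.

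Analyse percentage reduction in area twice: once with the blinded reviewers' area (0 cm² where they see complete re-epithelialisation), and once with the Investigator's closure call imputed as 0 cm². Prespecify which is the main analysis, preferably the blinded one, and which is the sensitivity analysis. Reporting both matters more than the order. List every subject for whom the two sources disagree. Leave the closure definition and the exit rule as they are.

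The cost is wording in the SAP, which Section 10 says is finalised before database lock, and one repeated analysis. The photographs and readers are already in place. The downside is a few discordant cases to explain, some arising because drainage and the need for a dressing cannot be judged from an image. Where the readers agree with the Investigator, both analyses use the same value.

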7.2 INCLUSION CRITERIA

Subjects will be considered qualified for enrollment if they meet the following criteria:

- Provide written informed consent, which will consist of reading, signing, and dating the informed consent document after the Investigator, sub-Investigator or other designated study staff member has explained the study procedures, risks, and contact information.
- 2. Eighteen years of age or older, of either sex, and of any race.

- 3. Willing to comply with protocol instructions, including allowing all study assessments.
- 4. Subject is in-patient in a long-term care facility.
- A pressure ulcer present with a surface area ≥ 1.0 cm² and ≤ 64.0 cm² confirmed using the ImageIQ EDCIQ mobile imaging system. Only one qualifying ulcer per subject will be selected for the study (selection based on greatest clinical need, as assessed by the Investigator).
- The target ulcer must present with ≥85% necrotic, nonviable tissue as assessed by at least one independent image reviewer.
- The target ulcer has not been previously treated with hydrogel (SoloSite[®]) or with SANTYL. Prior ulcers at or near the same location may have been treated with these products.
- No current infections requiring treatment with antibiotics (antibiotic use is permitted for the purpose of urinary tract infection prophylaxis, but this must be explicitly stated in the subject's chart).
- Acceptable state of health and nutrition with pre-albumin levels of ≥ 10 mg/dL (0.10 g/L), per the Screening local lab report. This is not required if a pre-albumin test within range has been conducted within the last 30 days.
- A hemoglobin A1c < 7.9% per the Screening local lab report. This is not required if a hemoglobin A1c test within range has been conducted within the last 30 days.

- Have adequate pressure redistribution to the affected area or off-loading if the ulcer is on a lower extremity.
- 12. No known allergies or sensitivities to either test article or the dressings.
- 13. Women of child-bearing potential (those who are not premenarchal, not surgically sterilized [hysterectomy or bilateral oophorectomy], or not post-menopausal), may participate in the study if they meet the following condition:
 - A negative urine pregnancy test at screening

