Two separate sensitivity analyses will be performed to ensure that the efficacy findings are not reliant on assumptions made in the analysis, derivations, or changes agreed between the blinded review panel. The analysis for the proportion of subjects achieving completed debridement will be repeated with the following modifications using the Full Analysis Set only:

- 1) In cases where there is initial disagreement (pre-consensus meeting) between the two blinded reviewers, the "worst case" value will be used. That is, in cases where one reviewer found the ulcer to have achieved complete debridement whilst the remaining reviewer found there to still be (>0%) necrotic, non-viable tissue present, the following will be imputed:

 Complete debridement achieved = No.
- 2) In cases where there is initial disagreement (pre-consensus meeting) between the two blinded reviewers, the "best case" value will be used. That is, in cases where one reviewer found the ulcer to have achieved complete debridement whilst the remaining reviewer found there to still be (>0%) necrotic, non-viable tissue present, the following will be imputed:

Complete debridement achieved = Yes.

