For purposes of the analysis, the assessment of percentage non-viable necrotic tissue will be assessed from photographs by two independent reviewers. The following analysis uses the mean of the two percentage non-viable tissue assessments conducted by the independent reviewers for each visit. In the event of disagreement between the two reviewers, the percentage non-viable necrotic tissue used in the following analysis will be the mean of the individual assessments of non-viable necrotic tissue after any consensus meetings have been conducted.

The reduction in the percentage non-viable necrotic tissue will be derived as:

Percentage non-viable necrotic tissue at Study Visit 1 – Percentage non-viable necrotic tissue at Study Visit 7

In cases where a photograph is not taken, the Last Observation Carried Forward (LOCF) method will be used. Sensitivity analyses will be conducted as detailed in the following sections.

The linear regression analysis described in the previous section to test for a difference between treatments in the percentage reduction in wound area over the 6-week will be repeated for the reduction in percentage of non-viable necrotic tissue over the 6-week treatment period. In addition, the separate analysis conducted to test for a difference in percentage reduction in

wound area between treatments between Visit 1 and Visits 2,3,4,5 and 6 will be repeated for the reduction in percentage of non-viable necrotic tissue at the stated time points.

The reduction in percentage non-viable necrotic tissue over the 6-week treatment period will be summarized by treatment separately by the covariates used in the final model. In addition, the percentage non-viable necrotic tissue and reduction percentage non-viable necrotic tissue at each study visit will be summarized by treatment separately by baseline percentage necrotic tissue [categorized] and overall.

Two separate sensitivity analyses will be performed to ensure that the efficacy findings are not reliant on assumptions made in the analysis, derivations or changes agreed between the blinded review panel. The previous section will be repeated with the following modifications using the Full Analysis Set only:

- The "worst case" value will be used. That is, the highest value of percentage non-viable necrotic tissue recorded by the two independent reviewers at each time point will be used for purposes of analysis.

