- 2) The "best case" value will be used. That is, the lowest value of percentage non-viable necrotic tissue recorded by the two independent reviewers at each time point will be used for purposes of analysis.

Change in Wound Status as measured by the PUSH and WBS tools following 6 weeks of treatment

Wound status will be measured by both the PUSH and WBS tools at Study Visit 1 and at Study Visit 7 (Exit).

At both Study Visit 1 and Study Exit, the PUSH Tool (version 3.0) will be scored according to the instructions for use (18.1.1). The sub-scores for Length/Width, Exudate Amount, and Tissue Type will be recorded. The Total Score, on a scale of 0-17, will then be derived by taking the sum of the three sub-scores detailed previously.

The reduction in PUSH individual sub-scores will be derived as follows; the reduction in Total Score will be derived using the same method:

PUSH Score at Visit 1 - PUSH Score at Exit Visit

A Wilcoxon Rank Sum test will be used to test for a difference between treatments in the reduction in Total PUSH Score over the 6-week treatment period.

The responses to the individual sub categories (Length/Width, Exudate Amount, and Tissue Type) will be summarized by treatment at each visit; in addition the reduction over the 6-week treatment period in each sub-score and total score will be summarized by treatment.

The WBS will be scored at the Study Visit 1 and Study Exit according to the instructions for use (18.1.2). The individual wound bed score characteristics, on a scale of 0-2, will be summed to derive the Total WBS on a scale of 0-16.

The reduction in Total WBS will be derived as follows:

Total WBS Score at Visit 1 - Total WBS Score at Exit Visit

A Wilcoxon Rank Sum test will be used to test for a difference between treatments in the reduction in Total WBS over the 6-week treatment period.

The responses to the individual wound bed score characteristics (Healing edges, Black eschar, etc.) will be summarized by treatment at each visit.

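### The 'worst case' and 'best case' analyses of non-viable tissue treat baseline like follow-up, so their labels can swap and the pair can be too narrow

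*Combined protocol and SAP*

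**What the plan says.** Section 10.3.2 derives the endpoint as the SV1 percentage minus the Study Visit 7 percentage. The main analysis uses the mean of the two image reviewers' values, after any consensus meeting. Two sensitivity analyses then repeat the whole analysis in the Full Analysis Set:

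- 'Worst case': "the highest value of percentage non-viable necrotic tissue recorded by the two independent reviewers at each time point will be used".
- 'Best case': "the lowest value of percentage non-viable necrotic tissue recorded by the two independent reviewers at each time point will be used".

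Part of their stated purpose is to show that findings do not depend on "changes agreed between the blinded review panel". The repeated outputs include the regression (with a treatment-only version), the unadjusted tests at Visits 2 to 6, and arm summaries in which tissue values and reductions "at each study visit will be summarized by treatment separately by baseline percentage necrotic tissue [categorized] and overall".

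Three other provisions matter:

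- **Readings at SV1.** Under Section 9.1.2 the share of necrotic, "nonviable tissue will be determined by two independent reviewers using the ImageIQ EDCIQ mobile imaging system". Section 7.2 requires at least 85% necrotic, "nonviable tissue as assessed by at least one independent image reviewer", so the second reading may be lower than 85%.
- **Consensus.** Section 9.4.2 calls a meeting only if one image reviewer records 0% "and the second reviewer does not, the photograph will be re-reviewed at a consensus meeting". Other disagreements, including those at SV1, stand.
- **The parallel pair for the primary endpoint.** Section 10.3.1 applies its rules "In cases where there is initial disagreement (pre-consensus meeting) between the two blinded reviewers" and imputes failure or success.

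On scale, the Synopsis, Section 5 and the opening of Section 10.3.2 speak of a percentage reduction. The subsection heading and formula in Section 10.3.2 give a difference in percentage points.

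**The concern.** More necrotic tissue at follow-up means a worse result. More necrotic tissue at SV1 means a larger reduction, which is a better result. A rule that takes the higher reading at both visits is therefore unfavourable at one end of the subtraction and favourable at the other. In the primary-endpoint pair, 'worst case' always gives the less favourable outcome; here it need not.

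An arm's 'worst case' table could show a larger mean reduction than its main table. Where readers differ at both visits, the pair would also understate how far reader disagreement could move that arm's result. Section 10.3.2 does not say whether these two analyses use readings from before or after consensus, so it is also unclear whether they test the panel's changes at all.

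**Working it through.** **Inputs.** The formula and the two rules come from Section 10.3.2, and the two SV1 readings from Section 9.1.2. Section 11 gives planning rates of 85% (SANTYL) and 29% (hydrogel) and 26 evaluable subjects, or 13 per arm. Those 26 reproduce: two-sided Fisher power is 80.9% at 13 per arm, if the unstated target is 80%. The plan gives no figure for reader variability, so all gaps and reader SDs below are assumptions.

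**Algebra.** Let b be the two SV1 readings and f the two follow-up readings.

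- 'Worst' = max(b) − max(f); 'best' = min(b) − min(f).
- 'Worst' − 'best' = gap(b) − gap(f).
- 'Worst' + 'best' = 2 × main value, if all three use the same readings.
- The readings allow min(b) − max(f) to max(b) − min(f), a width of gap(b) + gap(f).

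**Single ulcers (illustrative readings).**

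| SV1 | Follow-up | 'Worst' | 'Best' | Main | Range allowed |
|---|---|---|---|---|---|
| 100/85 | 0/0 | 100 | 85 | 92.5 | 85 to 100 |
| 100/85 | 20/10 | 80 | 75 | 77.5 | 65 to 90 |
| 88/92 | 10/40 | 52 | 78 | 65 | 48 to 82 |
| 90/90 | 5/15 | 75 | 85 | 80 | 75 to 85 |

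Row 1 gives the true extremes with the labels swapped. Row 2 is swapped and too narrow. Row 3 is labelled correctly but too narrow. Row 4, with agreement at SV1, is correct.

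**Arm means.** Suppose a proportion p of ulcers is read 0/0 at follow-up. Let g1 be the mean SV1 gap and g7 the mean follow-up gap in the other ulcers. Then mean 'worst' − mean 'best' = g1 − (1 − p) × g7. Taking p as the planning rate:

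| g1, g7 (assumed) | SANTYL: g1 − 0.15 × g7 | Hydrogel: g1 − 0.71 × g7 |
|---|---|---|
| 3, 20 | 0.0 | −11.2 |
| 5, 10 | +3.5 | −2.1 |
| 10, 5 | +9.25 | +6.45 |

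The labels swap for the arm mean when g1 exceeds 0.15 × g7 (SANTYL) or 0.71 × g7 (hydrogel).

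A simulation used 13 per arm and 4,000 runs, with reader SD 5 at both visits. True SV1 was uniform on 85 to 100 and non-debrided follow-up uniform on 10 to 80. The SANTYL mean was 87.2 'worst', 85.1 main and 83.1 'best', and the labels swapped in over 99% of runs.

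**Between arms.** Subtracting the two columns removes g1: ('worst' − 'best') for the treatment difference = (0.71 − 0.15) × g7 = 0.56 × g7, for equal g7 in both arms. SV1 photographs precede treatment and arms are randomized, so the SV1 rule does not shift the difference on average. In the simulation the difference was 26.8 under 'worst' and 23.7 under 'best', both as written and with SV1 held at its two-reader mean. In single trials the unadjusted 'worst' differences under those two SV1 rules differ by an SD of about 0.5 to 1.4 points (assumed SV1 reader SDs 3 to 10), against a standard error of about 9.

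**Baseline-adjusted model.** If the baseline covariate follows the same rule as the outcome, regressing b − f on treatment and b gives the same treatment coefficient as regressing −f on them. A numerical check agreed to rounding error.

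**Consensus.** Take SV1 100/85 and follow-up initially 0/20. Pre-consensus, 'worst' is 100 − 20 = 80 and 'best' is 85 − 0 = 85. If both readings then move to the agreed value, the main value is 92.5 (agreed 0%) or 72.5 (agreed 20%), outside the pair either way.

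**Scale.** A fall to 20% from 85% is 65 points, or 65/85 = 76.5%. From 100% it is 80 points, or 80%.

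**The case against.** The strongest defence is that 'highest' is a coherent label for the tissue level at any one visit, that the plan never promises bounds, and that inference barely changes. The covariate-adjusted model is the leading analysis and contains baseline non-viable tissue, so SV1 cancels or nearly cancels. This stands, and it limits the point to descriptive results and slight noise in the treatment-only model and visit tests. It does not rescue the labels, because the endpoint is a change score and the plan commits to arm summaries of it.

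Three stronger readings are tempting, and the documents do not support them:

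- **That the pair never gives the extremes.** It does when readers differ at only one visit, although with swapped labels if that visit is SV1.
- **That the rule inflates the treatment effect.** 'Worst case' does give the larger between-arm difference in the simulation, but this comes from the follow-up readings and remains when SV1 is held at its mean.
- **That the main value routinely falls outside the pair.** With the same readings it is exactly the midpoint. It can fall outside only if consensus changes a reading and the sensitivity analyses keep the earlier one.

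It is also fair to say that holding SV1 at its mean is no complete cure. In the simulation that SANTYL pair is 84.7 to 85.6, a width of 0.9 points against 4.1 as written, so it shows less reader uncertainty. The 15-point SV1 gap in the examples is illustrative and larger than the mean gaps of 3 to 10 assumed for the arms.

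**Conclusion.** The point holds within limits. As written, 'worst' minus 'best' equals the SV1 reader gap minus the follow-up reader gap. The labels swap whenever the SV1 gap is larger, which includes every ulcer read 0/0 at follow-up with differing SV1 readings. Where readers differ at both visits, the pair is narrower than the readings allow. These statements are exact.

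Their frequency and size depend on undocumented reader gaps. Over the assumed range, arm-mean 'worst' minus 'best' runs from 0.0 to about +9.3 points for SANTYL and from −11.2 to about +6.5 for hydrogel, if the planning rates hold and debrided ulcers are read 0% by both readers.

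The consequence is confined to sensitivity results for one secondary endpoint: mainly within-arm summaries, and slightly the treatment-only model and unadjusted visit tests. The average between-arm difference and the primary endpoint are unchanged, and the baseline-adjusted comparison is little affected.

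The scale mismatch is a separate, minor wording point. The formula is clear, but it is not the quantity the objective names.

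**What to change.** In the separate SAP that Section 10 says will be finalized before database lock, define per subject:

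- 'worst case' = lowest SV1 reading − highest follow-up reading;
- 'best case' = highest SV1 reading − lowest follow-up reading.

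Use pre-consensus readings, as Section 10.3.1 does, and hold the baseline covariate at the two-reader mean. In the consensus example this gives 85 − 20 = 65 and 100 − 0 = 100, which contains both possible main values. It does so generally if the agreed value lies between the two initial readings. For the simulated SANTYL arm, the widths above imply a mean SV1 gap of 4.1 + 0.9 = 5.0, so this pair would be about 5.0 + 0.9 = 5.9 points wide.

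The alternative is to hold SV1 at the two-reader mean in both analyses and state that the pair then tests follow-up disagreement only. Its drawback is that it shows no SV1 reader uncertainty and is narrower in an arm where most ulcers are read 0/0. Neither version bounds the treatment difference, because both arms move in the same direction, and the SAP should not describe the pair as doing so.

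Separately, put the objective and the formula on one scale and report the other as supportive. Together these are two short SAP entries and need no new data.
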